8.2. Withdrawal from the Study

Participants that are randomized but not dosed with study treatment will be considered for study withdrawal if Day 1 FBF measurement with ACh does not meet quality control criteria or they are unable to complete the initial FBF assessment, including a Day 1 FBF procedure where necessary (See Section 9.6.1.2). These participants will not be considered in the safety analysis as they have not received study treatment. Quality control procedures and criteria are described in the SRM. In all cases, the reason for withdrawal and the date of the last dose will be recorded in the participant's eCRF.

- A participant may withdraw from the study at any time at his/her own request, or may be withdrawn at any time at the discretion of the investigator for safety, behavioral, compliance or administrative reasons.
- If the participant withdraws consent for disclosure of future information, the sponsor may retain and continue to use any data collected before such a withdrawal of consent.
- If a participant withdraws from the study, he/she may request destruction of any samples taken and not tested, and the investigator must document this in the site study records.
- The participant will be asked to attend the follow-up visit 7 to 14 days following the last dose of study treatment. Refer to the SoA (See Section 2) for data to be collected at the time of follow-up and for any further evaluations that need to be completed.

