9.2.1. Time Period and Frequency for Collecting AE and SAE Information

- Any SAEs assessed as related to study procedure (e.g., protocol-mandated procedures, invasive tests, or change in existing therapy) or related to a GSK product will be recorded in the eCRF from the time a participant consents to participate in the study up to and including any follow-up contact.
- AEs and SAEs will be collected from randomization (Day 1) until the follow-up visit at the time points specified in the SoA (See Section [2](#)).
- Medical occurrences that begin before the start of study treatment but after obtaining informed consent will be recorded on the Medical History/Current Medical Conditions section of the eCRF and not the AE section.
- All SAEs will be recorded and reported to the sponsor or designee immediately and under no circumstance should this exceed 24 h, as indicated in [Appendix 4](#). The investigator will submit any updated SAE data to the sponsor within 24 h of it being available.
- Investigators are not obligated to actively seek AEs or SAEs in former study participants. However, if the investigator learns of any SAE, including a death, at any time after a participant has been discharged from the study, and he/she considers the event to be reasonably related to the study treatment or study participation, the investigator must promptly notify the sponsor.
- The method of recording, evaluating, and assessing causality of AEs and SAEs and the procedures for completing and transmitting SAE reports are provided in [Appendix 4](#).

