Sodium nitroprusside	Sodium nitroprusside directly causes vasodilation leading to decreases in blood pressure. Reported side effects of sodium nitroprusside administration are excessive hypotension and excessive accumulation of cyanide at high rates of infusion.	
 • Study undertaken only at specialist centers by experienced study personnel trained to conduct forearm blood flow assessment • Patients monitored continuously throughout technique • Minimum dose given for required physiological

Potential Risk of Clinical Significance	Summary of Data/Rationale for Risk	Mitigation Strategy
		response 
 • Patients with recent cardiovascular events excluded from the study
Study Procedures		
Venous occlusion plethysmography	Primary risk associated with venous venous occlusion plethysmography is related to the cannulation of the brachial artery. This has the potential for causing damage to the brachial artery, thrombosis, digital ischemia, and hemorrhage, as well as discomfort at the infusion site.	
 • Study undertaken only at specialist centers by experienced study personnel trained to conduct forearm blood flow assessment • Cannulation of the brachial artery for infusion of the challenge agents will be done with a fine (27 gauge) needle to minimize any injury to the artery • Cannulation will be done under a local anesthetic to minimize participant discomfort

References

- Campochiaro PA. Ocular versus extraocular neovascularization: mirror images or vague resemblances. *Invest Ophthalmol Vis Sci*. 2006; 47:462-74.
- Hofherr, A., *et al*, *HIF-1α drives cyst growth in advanced stages of autosomal dominant polycystic kidney disease*; *Kidney International* (2018) 94, 849–851.
- Kraus, A., *et al*, *HIF-1α promotes cyst progression in a mouse model of autosomal dominant polycystic kidney disease*; *Kidney International*, 2018.

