4. ANALYSIS POPULATIONS

Population	Definition / Criteria	Analyses Evaluated
Screened	
 • All participants who signed an ICF to participate in the clinical trial. This population will be used for summarizing screening failure rates and reasons for screening failure. 	
 • Screen Failures
Safety	
 • All randomized participants who receive at least one dose of study treatment will be included in the safety population. • This population will be used in the evaluation of all safety analyses • Participants will be analyzed according to the treatment received.¹ 	
 • Study population • Safety and tolerability
Pharmacodynamic Per-Protocol (PDPP) Population	
 • All randomized participants who provide pharmacodynamic (PD) data at Day 1 and Day 42 that meets the QC criteria (See Section 9.6.1.3 of Protocol) and completes the protocol without important deviations (exclusion are populated under 	
 • Primary, secondary endpoints

CONFIDENTIAL

205767

Population	Definition / Criteria	Analyses Evaluated
	
Section 10.1.1 of RAP) will be included in the PDPP population.
 
 • This population will be used in the evaluation of all endpoints with the exception of safety endpoints. • Participants will be analyzed according to the treatment received.¹ 	
Enrolled	
 • All randomized participants 	
 • Study population

[1]: Only participants receiving incorrect randomized treatment for the duration of their study participation will be analysed according to the treatment received. Otherwise, participants will be analyzed according to the treatment to which they were randomized.

Refer to [Appendix 10](#): List of Data Displays which details the population used for each display.

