7.1. Adverse Events Analyses

Adverse events analyses including the analysis of adverse events (AEs) and Serious (SAEs) will be based on GSK Core Data Standards. The details of the planned displays are provided in [Appendix 10: List of Data Displays](#).

Adverse Events

A listing of AE records for all participants who reported AEs will be produced.

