10.10.7. ICH Listings

ICH: Listings					
No.	Population	IDSL / Example Shell	Title	Programming Notes	Deliverable [Priority]
Subject Disposition					
1.	Screened	ES7	Listing of Reasons for Screen Failure	Journal Guidelines	SAC
2.	Enrolled	ES2	Listing of Reasons for Study Withdrawal	ICH E3	SAC
3.	Safety	SD2	Listing of Reasons for Study Treatment Discontinuation	ICH E3	SAC

CONFIDENTIAL

205767

ICH: Listings					
No.	Population	IDSL / Example Shell	Title	Programming Notes	Deliverable [Priority]
Protocol Deviations					
4.	Safety	DV2	Listing of Important Protocol Deviations	ICH E3	SAC
5.	Safety	IE3	Listing of Participants with Inclusion/Exclusion Criteria Deviations	ICH E3	SAC
Demographic Characteristics					
6.	Safety	DM2	Listing of Demographic Characteristics	ICH E3	SAC
Prior and Concomitant Medications					
7.	Safety	CM10	Listing of Concomitant Medications	IDSL	SAC
8.	Safety	MH2	Listing of Medical Conditions	IDSL	SAC
Exposure					
9.	Safety	EX3	Listing of Exposure Data	ICH E3	SAC
Adverse Events					
10.	Safety	AE8	Listing of All Adverse Events	ICH E3	SAC
Serious Adverse Events					
11.	Safety	AE14	Listing of Reasons for Considering as a Serious Adverse Event	ICH E3	SAC
12.	Safety	AE8	Listing of Adverse Events Leading to Withdrawal from Study / Permanent Discontinuation of Study Treatment	ICH E3	SAC
All Laboratory					
13.	Safety	LB5	Listing of All Laboratory Data for Participants with Any Value of Potential Clinical Importance/Outside Normal Range	ICH E3	SAC
14.	Safety	LB14	Listing of Laboratory Data with Character Results	ICH E3	SAC

CONFIDENTIAL

205767

ICH: Listings					
No.	Population	IDSL / Example Shell	Title	Programming Notes	Deliverable [Priority]
ECG					
15.	Safety	EG5	Listing of All ECG Findings for Participants with an Abnormal ECG Finding	IDSL	SAC
Vital Signs					
16.	Safety	VS4	Listing of All Vital Signs Data for Participants with Any Value of Potential Clinical Importance	IDSL	SAC

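### Events from the Day 1 arterial procedure in randomised participants who are never dosed appear in no planned display that describes them, and the protocol's recording rule for pre-dose events conflicts with itself

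*Protocol*

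**What the plan says.** Protocol 8.2 covers people who are randomised and then fail at the first forearm blood flow (FBF) session, either because their acetylcholine data miss the quality criteria or because they cannot finish the session. Such people, still undosed, may be withdrawn. It then adds: "These participants will not be considered in the safety analysis as they have not received study treatment".

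The SAP builds its populations to match. Section 4 states: "All randomized participants who receive at least one dose of study treatment will be included in the safety population". It also says: "This population will be used in the evaluation of all safety analyses". The same section defines an Enrolled population, which is everyone randomised.

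SAP 10.10.7 plans three AE displays: Listing 10 ("Listing of All Adverse Events"), Listing 11 (reasons for classing an event as serious) and Listing 12 (events leading to withdrawal or discontinuation). Each has Safety in its population column. The safety tables in SAP 10.10.5 (2.1 to 2.9) cover laboratory, ECG and vital signs data and include no AE table.

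On collection, Protocol 9.2.1 states: "AEs and SAEs will be collected from randomization (Day 1) until the follow-up visit". The next bullet in that section sends occurrences that begin after consent but before the start of study treatment to the Medical History page instead of the AE page.

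**The concern.** A dosed safety population is the usual choice when the only hazard is the study drug. In this trial an invasive, protocol-mandated procedure comes between randomisation and the first dose. Protocol Appendix 7 treats it as a risk in its own right and says of the cannulation: "This has the potential for causing damage to the brachial artery, thrombosis, digital ischemia, and hemorrhage, as well as discomfort at the infusion site". It also lists blood pressure effects for the challenge agents.

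Inability to complete that procedure is one of the two routes by which a participant leaves undosed under 8.2, so the exclusion is tied to how the procedure went. If such a participant had a procedural event, the study report would carry no description of its term, severity or causality. The recording conflict in 9.2.1 raises a second possibility: events at the Day 1 session may not be on the AE page at all, even for participants who went on to treatment.

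**Working it through.** No arithmetic is involved beyond a count of displays. The check sets the sequence of events against the population of each display.

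**1. Sequence.** The Schedule of Activities places randomisation on Day 1 and, in footnote 10, the first dose after the completed Day 1 or Repeat Day 1 procedures. Protocol 9.6.1.2 allows one further attempt up to a week later, still undosed. A participant can therefore be randomised, cannulated and infused, possibly twice, and never dosed.

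**2. Status of the challenge agents.** Protocol 7 defines study treatment broadly, but 7.1.1 and 7.1.2 list study treatments and challenge agents separately. Protocol 8.2 describes participants whose acetylcholine data failed quality control as not having received study treatment. A challenge infusion does not bring anyone into the Safety population.

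**3. Displays that could describe an event.**

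| Display (SAP Appendix 10) | Population | Describes an event in an undosed participant? |
|---|---|---|
| Listing 10, all AEs | Safety | No |
| Listing 11, seriousness reasons | Safety | No |
| Listing 12, AEs leading to withdrawal or discontinuation | Safety | No |
| AE summary tables | None planned | No |
| Listing 8, medical conditions | Safety | No |
| Listing 2, withdrawal reasons | Enrolled | Reason only, no AE detail |
| Tables 1.3 and 1.5, site counts and age ranges | Enrolled | No |

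AE displays on Safety: 3 of 3. AE displays on Enrolled: 0 of 3.

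**4. Recording rule.** Two bullets of Protocol 9.2.1 apply to a non-serious event at the Day 1 session. One says AEs are collected from randomisation, which puts the event on the AE page. The other says occurrences before the start of treatment are Medical History, which keeps it off. Protocol Appendix 4 leans to the second reading, since it defines an AE by temporal association with use of a study treatment and says that what is not an AE cannot be serious. Yet 9.2.1 also requires procedure-related serious events to be recorded from consent. The three rules cannot all be applied as written.

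**5. Consequence.** If sites followed the Medical History bullet, moving Listings 10 to 12 to Enrolled would not by itself show these events. For a dosed participant the event would appear in Listing 8 as a medical condition. For an undosed participant it would appear in neither listing.

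**The case against.** The strongest reply is that the documents are consistent and the choice is deliberate. Protocol 10.3.2 and the opening of SAP 7 both put safety data on the Safety population, and that set is the right one for attributing events to study treatment. This stands, and the Safety population should stay as it is. The point here is only that a second, separately recognised source of harm needs somewhere to be reported.

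A reader might infer more than the documents support in four respects.

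- **That SAP 7.1 contradicts the display list.** It says: "A listing of AE records for all participants who reported AEs will be produced". But 7.1 sits under the Section 7 rule that safety analyses use the Safety population unless otherwise specified, and it refers to Appendix 10 for the displays. Read in place, it means all such participants within that population. The same answer applies to SAP 10.7.1, whose promise to list withdrawn participants' data also yields to a specific rule.
- **That the events are lost altogether.** They are not. Procedure-related serious events are recorded from consent, serious events go to the sponsor within 24 hours, and Listing 2 may show a withdrawal reason. A participant who fails Day 1, completes the repeat and is then dosed does enter the Safety population.
- **That procedural harm is materially under-reported.** Nothing says that any randomised participant went undosed. The SAP mentions only 4 completed subjects. The 8.2 exclusion also covers data-quality failures, and these participants are only considered for withdrawal. That they are especially likely to have had a procedural event is plausible but not documented.
- **That the incidence and severity endpoint cannot be reported without a count table.** Protocol 10.3.2 plans listings by treatment and no formal safety analysis. With so few participants, counts for the dosed group can be read from Listing 10.

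**Conclusion.** The concern holds as a reporting gap created by an explicit rule. Under the plan as written, an event from the Day 1 procedure in a randomised, never-dosed participant would be described in none of the three AE displays, nor in the medical conditions listing. Separately, the bullets in Protocol 9.2.1 give conflicting instructions for pre-dose events, so Day 1 procedural events could miss the AE listings in dosed participants too.

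The number of events affected cannot be computed and may be zero. The sponsor can get the number of participants at issue directly: the total in Table 1.3 (Enrolled) minus the Safety population count. Power, type I error and the pharmacodynamic summaries are not touched. The conclusion rests on the SAP's population column being applied as printed, and on challenge agents not counting as study treatment, which Protocol 8.2 implies.

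**What to change.** 1. In SAP 10.10.7, change the population of Listings 10, 11 and 12 from Safety to Enrolled, with a separate block for participants randomised but not dosed. Flag events that begin before the first dose or are attributed to the procedure or a challenge agent. The study phases in SAP 10.4.1 need a treatment start date, so the block label would stand in for the phase in undosed participants.
2. Qualify the Protocol 8.2 sentence: these participants are left out of summaries of study-treatment safety, but their events are still listed. As the study has been terminated, an entry in the SAP 2.1 table of changes would serve.
3. Reconcile the 9.2.1 bullets, together with the Appendix 4 definition, so that procedure and challenge-agent events from randomisation onward are recorded as AEs. Where such events are already held as Medical History, extend Listing 8 to Enrolled so that they are shown.

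A table of AE counts is optional and is not needed to close this point.

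The cost is a change to the population column, a little extra programming, and a check of existing AE and Medical History records for Day 1 events. No new data collection is needed, and the Safety population is unchanged.

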2. SCHEDULE OF ACTIVITIES (SOA)

Procedure	Screening ¹	Treatment Period ²						Follow-up ³
	Up to 30 Days	Day 1	Repeat Day 1 ¹⁷	Day 14	Day 28	Day 42	Repeat Day 42 ¹⁷	
Informed consent	X							
Eligibility Criteria	X	X ⁴						
Physical examinations, Medical History, Demographics	X	X ⁵						
HemoCue Hgb	X	X ⁶	X	X	X	X	X	
eGFR	X							
Vital signs	X	X ⁶	X	X	X	X	X	X
Clinical chemistry ⁷	X					X		X
Hematology ⁷	X	X		X	X	X		X
Serum pregnancy test (FRP only)	X							
Urine pregnancy test (FRP only) ⁸		X	X	X	X	X	X	X
Folate & Vitamin B ₁₂	X							
12 Lead ECG	X	X ⁶				X		X
Ferritin & TSAT	X							
hs-CRP	X	X				X		
Females only: FSH ⁹	X							
Brachial artery palpation	X							
Randomization		X						
Daprodustat administration ¹⁰		<=====>						
Darbepoetin alfa administration ¹⁰		X ¹⁰		X	X	See footnote 18		
Study treatment adjustment ¹¹					X			
Liver chemistry monitoring				X	X			
International Normalized Ratio (INR) ¹²	X	X	X			X	X	

Procedure	Screening ¹	Treatment Period ²						Follow-up ³
	Up to 30 Days	Day 1	Repeat Day 1 ¹⁷	Day 14	Day 28	Day 42	Repeat Day 42 ¹⁷	
Hepatitis B and C screening ¹³	X							
HbA1c, lipids ⁷		X						
Forearm Blood Flow (FBF) ¹⁴		X	X			X	X	
Pulse Wave Velocity (PWV) ¹⁴		X	X			X	X	
AE and SAE Assessment	X ¹⁵	X	X	X	X	X	X	X
Blood draw for storage biomarkers ¹⁶		X				X		
Review concomitant medications	X	X	X	X	X	X	X	X

¹All participants will undergo screening assessments within 30 days of enrolment.

²Allowable time window \pm 2 days except for the forearm blood flow (FBF) & pulse wave velocity (PWV) as noted.

³Allowable time window \pm 3 days. Follow up will occur 7-14 days \pm 3 following completion of the last FBF procedure. See Section 8.2 for guidance regarding EW participants.

⁴Eligibility criteria to be assessed prior to performance of the FBF procedure include HemoCue hemoglobin (Hgb), vital signs & 12-lead electrocardiogram (ECG).

⁵Only a brief physical exam on Day 1.

⁶As detailed in Exclusion Criteria (Section 6.2).

⁷Clinical chemistry, hematology and other laboratory tests as listed in Appendix 2.

⁸Local urine pregnancy testing will be standard for protocol unless serum testing is required by local regulations or Institutional Review Board (IRB)/ Independent Ethics Committee (IEC).

⁹As detailed in Inclusion Criteria (Section 6.1).

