7.1.1.2. Darbepoetin Alfa Dosing Information

Darbepoetin alfa will be administered subcutaneously (SC) once every two weeks starting **after** the completion of the FBF & PWV procedures on Day 1.

Darbepoetin Alfa Starting Dose and Dose Adjustments

Participants randomized to darbepoetin alfa will receive study treatment according to local labelling, clinical practice guidelines, and clinical judgement to maintain Hgb in the target range (10.0-12.0 g/dL). For additional guidance on Hgb-based stopping criteria please refer to Section 8.1.2. Darbepoetin alfa is to be administered as a single subcutaneous injection once every two weeks as outlined in the SoA (See Section 2), although doses can be temporarily held or delayed if necessary to maintain patient safety (after consultation with the study medical monitor). Doses can only be modified on Day 28 as noted in the SoA (See Section 2).

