8.1.2. Hgb Stopping Criteria

GSK will supply a point-of-care Hgb analyzer (HemoCue) to each site for rapid and convenient monitoring of Hgb levels and to ensure consistency of Hgb measurements across sites participating in the study.

Blood samples for measurement of Hgb concentrations via HemoCue will be collected and recorded in the eCRF. [Table 2](#) summarizes the Hgb values and corresponding action to be taken at each visit.

Table 2 Hgb Stopping Criteria

Hgb (g/dL) at visit		Action
<7.5		Repeat HemoCue assessment on the same sample at same study visit to confirm; take average of 2 values. If confirmed, permanently discontinue study treatment and withdraw participant from the study.
≥7.5 - <13.0 with:	≥2.0 g/dL decrease in Hgb over the previous 2 weeks	Repeat HemoCue assessment on the same sample at same study visit to confirm; take average of 2 values. If confirmed, permanently discontinue study treatment and withdraw participant from the study.
≥7.5 - <13.0 with:	≥1.3 g/dL increase in Hgb over the previous 2 weeks (at Day 15 only) ¹	Repeat HemoCue assessment on the same sample at same study visit to confirm; take average of 2 values. If confirmed, permanently discontinue study treatment and withdraw participant from the study.
≥13.0		Repeat HemoCue assessment on the same sample at same study visit to confirm; take average of 2 values. If confirmed, permanently discontinue study treatment and withdraw participant from the study.

¹ If increase in Hgb >1.3 g/dL is noted on Day 28, refer to Dose Modification (Section 7.2).

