9. STUDY ASSESSMENTS AND PROCEDURES

- Study procedures and their timing are summarized in the SoA (See Section 2).
- Protocol waivers or exemptions are not allowed.
- Immediate safety concerns should be discussed with the sponsor immediately upon occurrence or awareness to determine if the participant should continue or discontinue study treatment and be withdrawn.
- Adherence to the study design requirements, including those specified in the SoA (See Section 2), is essential and required for study conduct.
- All screening evaluations must be completed and reviewed to confirm that potential participants meet all eligibility criteria. The investigator will maintain a screening log to record details of all participants screened and to confirm eligibility or record reasons for screening failure, as applicable.
- Procedures conducted as part of the participant's routine clinical management (e.g., Hgb levels) and obtained before signing of the ICF may be utilized for screening or baseline purposes provided the procedure met the protocol-specified criteria and was performed within the time frame defined in the SoA (See Section 2).
- The maximum amount of blood collected from each participant over the duration of the study, including any extra assessments that may be required, will not exceed 500 mL.
- Repeat or unscheduled samples may be taken for safety reasons or for technical issues with the samples.

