9.2.3. Follow-up of AEs and SAEs

After the initial AE/SAE report, the investigator is required to proactively follow each participant at subsequent visits/contacts. All SAEs, and non-serious AEs of Special Interest (AESI; as defined in Section 9.2.5), will be followed until the event is resolved, stabilized, otherwise explained, or the participant is lost to follow-up (as defined in Section 8.3). Further information on follow-up procedures is given in Appendix 4.

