9.4.4. Clinical Safety Laboratory Assessments

- Refer to [Appendix 2](#) for the list of clinical laboratory tests to be performed and to the SoA (See Section 2) for the timing and frequency.
- The investigator must review the laboratory report, document this review, and record any clinically relevant changes occurring during the study in the AE section of the eCRF. The laboratory reports must be filed with the source documents. Clinically significant abnormal laboratory findings are those which are not associated with the underlying disease, unless judged by the investigator to be more severe than expected for the participant's condition.
- All laboratory tests with values considered clinically significantly abnormal during participation in the study or within 14 days after the last dose of study treatment should be repeated until the values return to normal or baseline or are no longer considered significantly abnormal by the investigator or medical monitor.
- If such values do not return to normal/baseline within a period of time judged reasonable by the investigator, the etiology should be identified and the sponsor notified.
- All protocol-required laboratory assessments, as defined in [Appendix 2](#), must be conducted in accordance with the laboratory manual and the SoA (See Section 2).

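### Early-withdrawal follow-up is counted from the last dose, so a darbepoetin participant withdrawn just before an injection has 0 to 1 day of window left (3 to 4 if ±3 applies), against 13 to 14 (16 to 17) on daprodustat

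*Protocol*

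**What the plan says.** Protocol Section 8.2 times the early-withdrawal visit from the last dose: "The participant will be asked to attend the follow-up visit 7 to 14 days following the last dose of study treatment". It gives no tolerance, no arm-specific rule and no minimum interval after the withdrawal itself.

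The Schedule of Activities (Section 2, footnote 3) gives the follow-up column ±3 days and times the visit differently for participants who reach the end of treatment, namely "following completion of the last FBF procedure. See Section 8.2 for guidance regarding EW participants". Whether the ±3 days carries over to early withdrawals is left open.

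The other provisions that matter are these:

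- **Dosing.** Daprodustat is daily from Day 1 to Day 41. Darbepoetin is given on Days 1, 14 and 28 (Synopsis; Section 7). Under Section 7.1.1.2, darbepoetin "doses can be temporarily held or delayed if necessary to maintain patient safety", after consulting the medical monitor.
- **Stopping.** Section 8.1.2 applies the hemoglobin criteria at each visit, and a confirmed breach means stopping treatment and leaving the study. Section 8.1 makes every treatment discontinuation a withdrawal. One row of Table 2 refers to an "increase in Hgb over the previous 2 weeks (at Day 15 only"; the Schedule of Activities has no Day 15 visit.
- **Adverse events.** Section 9.2.1 states that "AEs and SAEs will be collected from randomization (Day 1) until the follow-up visit at the time points specified in the SoA".

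**The concern.** The stopping rules act at visits that are also darbepoetin injection days. If the hemoglobin check leads to withdrawal before the injection, the last darbepoetin dose is already about two weeks old and the 7-to-14-day window is nearly or fully used up. On daprodustat the last tablet was taken that day or the day before, so almost the whole window is still ahead. One rule thus gives the two arms very different periods of observation after withdrawal.

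What is at stake is safety information. In the Schedule of Activities, ECG falls at screening, Day 1, Day 42 and follow-up, and full chemistry at screening, Day 42 and follow-up. For someone withdrawn on Day 14 or Day 28, the follow-up visit therefore supplies the only ECG after Day 1, the only full chemistry after screening and the only scheduled hemoglobin after withdrawal. That participant may have been withdrawn because of hemoglobin. As written, the visit can coincide with the withdrawal visit, and active collection of new adverse events can end there.

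**Working it through.** The plan states no figure for days remaining, so there is none to reproduce. The check is calendar arithmetic on the stated window and dosing days.

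**Inputs.** Window 7 to 14 days after the last dose (Section 8.2). Possible extra 3 days (Section 2, footnote 3). Darbepoetin on Days 1, 14 and 28; daprodustat daily (Synopsis; Section 7). Treatment visits ±2 days (Section 2, footnote 2). Assumption: the HemoCue check comes before the injection.

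**Formula.** Days until the window closes = last dose day + 14 (+3 if the allowance applies) − withdrawal day.

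| Case | Last dose | Calculation | Nominal | With +3 |
|---|---|---|---|---|
| Darbepoetin, Day 14 | Day 1 | 1 + 14 − 14 | 1 | 4 |
| Darbepoetin, Day 15 (Table 2 label) | Day 1 | 1 + 14 − 15 | 0 | 3 |
| Darbepoetin, Day 28 | Day 14 | 14 + 14 − 28 | 0 | 3 |
| Darbepoetin, Day 28, Day 14 dose held | Day 1 | 1 + 14 − 28 | −13 | −10 |
| Daprodustat, Day 14, tablet the day before | Day 13 | 13 + 14 − 14 | 13 | 16 |
| Daprodustat, Day 14, tablet the same day | Day 14 | 14 + 14 − 14 | 14 | 17 |
| Daprodustat, Day 28, tablet the day before | Day 27 | 27 + 14 − 28 | 13 | 16 |
| Daprodustat, Day 28, tablet the same day | Day 28 | 28 + 14 − 28 | 14 | 17 |

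A negative figure means the window closed before the participant was withdrawn.

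**When the window opens** (last dose day + 7 − withdrawal day). Darbepoetin Day 14: 1 + 7 − 14 = −6. Darbepoetin Day 28: 14 + 7 − 28 = −7. The window is therefore already open 6 to 7 days before withdrawal. Daprodustat Day 28: 27 + 7 − 28 = 6 or 28 + 7 − 28 = 7. The daprodustat visit thus falls 6 to 14 days after withdrawal, or 3 to 17 with ±3.

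**Visit tolerance of ±2 days.**

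- Darbepoetin Day 14 visit held on Day 12: 1 + 14 − 12 = 3. Held on Day 16: 1 + 14 − 16 = −1. With +3, the range is 6 to 2.
- Darbepoetin Day 28, earlier dose on Day 16 and visit on Day 26: 16 + 14 − 26 = 4. Dose on Day 12 and visit on Day 30: 12 + 14 − 30 = −4. With +3, the range is 7 to −1.

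**Completers, for comparison.** Follow-up 7 to 14 days after a Day 42 procedure is Day 49 to 56. That is 49 − 28 = 21 to 56 − 28 = 28 days after the last darbepoetin dose, and 49 − 41 = 8 to 56 − 41 = 15 days after the last daprodustat dose.

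**The case against.** **The rule equalizes time since exposure.** Counting from the last dose sees both arms 7 to 14 days after their last treatment. The laboratory rule in Section 9.4.4 also uses a last-dose anchor: "All laboratory tests with values considered clinically significantly abnormal during participation in the study or within 14 days after the last dose of study treatment" are to be repeated. This is a coherent alternative, but the protocol states no such rationale, and completers are not handled that way.

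**The ±3 days may apply.** Footnote 3 sits on the whole follow-up column, and its tolerance is not restricted to completers. That is a reasonable reading. It leaves 3 to 4 days on darbepoetin and allows a separate visit, but it does not rescue the held-dose case.

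**13 to 14 days is a latest date, not a guarantee.** With ±3, a daprodustat visit could fall 3 days after withdrawal, which meets the top of the darbepoetin range. This stands: the permitted ranges touch, although they remain very different.

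**The group is narrow.** It needs darbepoetin, withdrawal at a dosing visit, and withdrawal before the injection. Stops on central laboratory results would usually come after the injection. The Day 15 row may be a slip for Day 14. The documents give no distribution of withdrawal times, so the number affected is unknown.

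**Other provisions cover much of the gap.** Clinically significant abnormal laboratory values found during participation, including a hemoglobin that triggers withdrawal, are repeated (Section 9.4.4; Appendix 2). Section 9 adds: "Repeat or unscheduled samples may be taken for safety reasons or for technical issues with the samples". SAEs and non-serious AEs of special interest "will be followed until the event is resolved, stabilized, otherwise explained, or the participant is lost to follow-up" (Section 9.2.3). Liver events have their own monitoring (Appendix 6), and pregnant participants keep attending visits (Appendix 5). A related SAE that the investigator learns of after discharge must still be notified (Section 9.2.1). All this reduces the loss. Apart from the pregnancy rule, these provisions respond to a problem already known or are optional; none schedules a later look for new events.

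**The trial has ended.** SAP Section 2.1 records termination with four completed subjects, so the amendment can no longer help this study.

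**Conclusion.** The concern holds, at minor weight. For a darbepoetin participant withdrawn at a dosing visit before the injection, the follow-up window has 0 to 1 day left on nominal days (3 to 4 with the allowance), against 13 to 14 (16 to 17) on daprodustat. If the Day 14 dose was held, an in-window visit after a Day 28 withdrawal is impossible on either reading. Withdrawals soon after an injection are not affected.

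This rests on the HemoCue check preceding the injection. The protocol does not say so outright, but a stopping rule applied at a dosing visit implies that order.

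The damage is limited to safety observation after withdrawal. If a site holds the visit late, adverse event collection continues and the cost is a timing deviation. The primary endpoint needs Day 42 data (Section 10.2), safety has no formal analysis (Section 10.3.2), and treatment-emergent flags stop one day after treatment ends (SAP Section 10.4.2). None of these changes.

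**What to change.** In Section 8.2, schedule the follow-up visit 7 to 14 days (±3) after the later of the withdrawal visit and the last dose, in both arms. This also settles whether the ±3 days applies. The window would then open 7 days after a dosing-visit withdrawal and close at 14 in either arm (4 and 17 with ±3).

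The cost is one sentence and no new visit; some darbepoetin early-withdrawal visits move one to two weeks later. The trade-off is that time since last dose would no longer match between arms (figures without the ±3):

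- Darbepoetin, Day 14 withdrawal: 14 + 7 − 1 = 20 to 14 + 14 − 1 = 27 days.
- Darbepoetin, Day 28 withdrawal: 28 + 7 − 14 = 21 to 28 + 14 − 14 = 28 days.
- Darbepoetin, Day 14 dose held, Day 28 withdrawal: 28 + 7 − 1 = 34 to 28 + 14 − 1 = 41 days.
- Daprodustat: 28 + 7 − 28 = 7 to 28 + 14 − 27 = 15 days.

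Apart from the held-dose case, this is close to what completers already have. With the study terminated, the change is useful mainly wherever this withdrawal text is reused.
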